1. LIST OF ABBREVIATIONS

Abbreviation	Definition
ADR	adverse drug reaction
AE	adverse event
AEM	adverse event monitoring
ANC	absolute neutrophil count
CRF	case report form
CRP	C-reactive protein
CYP	cytochrome P450
EDP	exposure during pregnancy
ESR	erythrocyte sedimentation rate
GEP	Good Epidemiological Practice
GPP	Good Pharmacoepidemiology Practice
HDL	high density lipoprotein
IEA	International Epidemiological Association
IEC	Independent Ethics Committee
IRB	Institutional Review Board
ISPE	International Society for Pharmacoepidemiology
LDL	low density lipoprotein
MFDS	Ministry of Food and Drug Safety
NIS	non-interventional study
PhRMA	Pharmaceutical Research and Manufacturers Association
PMS	post-marketing surveillance
pANCA	perinuclear anti-neutrophil cytoplasmic antibodies
SAE	serious adverse event
SAP	statistical analysis plan
SRSD	single reference safety document
TC	total cholesterol
UC	ulcerative colitis
VAS	visual analogue scale
MedDRA	Medical Dictionary for Regulatory Activities

3. AMENDMENTS AND UPDATES

Amendment number	Date	Protocol section(s) changed	Summary of amendment(s)	Reasons
Amendment 1	23 Jul 2019	2. Responsible parties	Change of responsible parties	NISL change
		5. Rationale and background	Least number of patients to be followed until the end of 52 weeks mentioned	Amendment recommended by the MFDS
		7.1. Study design	Included how to clinically assess the efficacy Added the content of the follow-up for long-term users.	
		7.2.5. Study Procedures 7.2.5.1. Basic Information	Added the content of the follow-up for long-term users	
		7.2.5.2. Demography and baseline characteristics	Included Partial Mayo Score	
		7.3.1. Safety variables 7.3.2. Efficacy variables 7.3.3. Efficacy evaluation	Added the content of the follow-up for long-term users	
		7.7.2. Efficacy analysis		

Amendment 2	26 Aug 2019	7.3.1.1. Adverse event	Added the 'not applicable' in the Causality assessment	Amendment recommended by the MFDS
		7.7.1. Safety analysis	Added the definition of patients entering this study for the safety analysis Described the special populations in detail	
		7.7.2 Efficacy analysis	Added the definition of the patients entering this study for the efficacy analysis Added the efficacy analysis for incompletely long-term users	
		7.7.4. Statistical consideration	Described the statistical analysis in detail	
Amendment 3	19 Sep 2019	7.3.2. Efficacy variables 7.3.3. Efficacy evaluation	Added the final efficacy variable in efficacy variables	Added the final efficacy variable by investigator
Amendment 4	15 Oct 2019	7.1. Study design	Removed the Truelove and Witt's Score	Mayo score is more frequently used in actual medical practice
		7.3.1.1. Adverse events 7.6. Data management	Changed the criteria of AE terminology from the WHO-ART to MedDRA	Changed for digitalization and standardization of AE terminology
		7.3.2. Efficacy variables 7.3.3. Efficacy evaluation	Clarified the final efficacy evaluation	To reflect the actual medical practice

Amendment 5	06 Feb 2020	4.Milestones	Add RMP report submission timeline	Amended according to the MFDS comments	
		7.7.1.Safety analysis	Add analysis and evaluation methods for safety specification according to RMP		
Amendment 6	23 Mar 2021	5. Rationale and background	Modify number of patients in the study	Change of research methods	
		7.1 Study design	Add retrospective data collection method		
		7.2.1. Inclusion criteria			
		7.2.5. Study procedures			
		7.2.5.1. Basic information			
		7.2.5.2. Demography and baseline characteristics			
Amendment 7	25 Mar 2022	Total	Change 'Efficacy' to 'Effectiveness' if it is evaluated under usual clinical practice	To clarify the definition of terms	
		5. Rationale and background	Remove retrospective data collection method		
		7.1 Study design			

		7.2.1. Inclusion criteria		
		7.2.5. Study procedures		
		7.2.5.1. Basic information		
		7.2.5.2. Demography and baseline characteristics		
	7.3.1.2. Laboratory test	Remove laboratory normal ranges of the center	Change of data collection methods	
	7.4.2. Record retention	Add record retention period	To align with regulation	
	7.5. Study Size	Modify number of patients in the study	Change of research methods	

4. MILESTONES

Milestone	Planned date
Start of data collection	27 May 2019
End of data collection	19 September 2022
First year (1-1) periodic report (MFDS)	19 May 2019
First year (1-2) periodic report (MFDS)	19 November 2019
Second year (2-1) periodic report (MFDS)	19 May 2020
Second year (2-2) periodic report (MFDS)	19 November 2020
Third year annual report (MFDS)	19 November 2021
Final study report (MFDS)	19 December 2022

- Abbreviations: MFDS=Ministry of Food and Drug Safety.

- RMP periodic report will be submitted every year after RMP approval, and final report will be submitted after December 2022 considering completion schedule of xeljanz post-marketing surveillance final report in patients with ulcerative colitis.

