7.2.3. Duration of the study

According to the MFDS re-examination regulation, the analyzed study report based on 4 years of collected data has to be submitted to MFDS within 3 months after the end of specified re-examination period (from the indication approval date to 4 years afterwards). The re-examination period is from 20 September 2018 to 19 September 2022, and the final study report should therefore be submitted by 19 December 2022.

CCI [REDACTED]

[REDACTED]

[REDACTED]

CCI [REDACTED]

[REDACTED]

CCI

CCI

CCI

CCI

CCI

CCI

CC1

CCI

CCI

CC1

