7.2.5. Study procedures

Patients will be enrolled by continuous registration method. The investigator should enroll all patients to whom Xeljanz is prescribed for the first time according to the local product label and who agree to participate in this study by signing the data privacy statement (used in place of the informed consent form). Xeljanz will be medicated by the investigator's prescription under usual clinical practice. Pfizer Korea will not provide the medicinal product for this study.

There will be no mandatory visit during the study. The investigators will collect relevant data from the time of initiating administration of Xeljanz until 24 weeks of treatment (52 weeks of treatment for the long-term users). If the patient does not complete 24 or 52 weeks of treatment, relevant data should be collected based on the last assessment performed at the time of treatment discontinuation. The investigator should record the following information on the patient's CRF.

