7.7. Data analysis

Analysis will be performed for the pooled data collected by each investigator during the re-examination period. Total number of centers participating, total number of cases enrolled and retrieved, and total number of cases included in the analysis will be presented in summary tables. Evaluation of data will primarily consist of summary displays (eg, descriptive statistics, tables, and graphs).

Detailed methodology for summary and statistical analyses of data collected in this study will be documented in a Statistical Analysis Plan (SAP), which will be dated, filed and maintained by Pfizer. The SAP may modify the plans outlined in the protocol; any major modifications of primary endpoint definitions or their analyses will be reflected in a protocol amendment.

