### 3.2. Efficacy Analysis Set

The Efficacy analysis set will be included all patients entering this study for the safety analysis whose efficacy data are available after 24 weeks of treatment, or based on the last assessment performed at the time of treatment discontinuation if the patient does not complete the 24 weeks of treatment. If the patient does not complete the 24 weeks of treatment, the cause of discontinuation will be assessed.

The cases below shall be excluded from the efficacy analysis set in the following order:

- 1) Subjects who are excluded from the safety analysis set
- 2) Subjects without general efficacy assessment by the investigator
- 3) Subjects who are evaluated general efficacy assessment as 'Not assessable' by the investigator
- 4) Subjects who are have been administrated Xeljanz® for less than 8 weeks (56 days)

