## **4. Study Endpoints**

### 4.1. Safety Endpoints

Safety will be assessed by the investigator based on all AEs that occur during the 24 weeks (52 weeks for the long-term users) from the first treatment for all patients who have received at least 1 dose of Xeljanz® according to the local product document.

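### The primary AE incidence is a crude proportion over unequal follow-up (cut short by the calendar, 24 weeks, 52 weeks), so it describes no defined time window

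*Protocol*

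**What the plan says.** **Calendar.** Protocol section 4 gives "Start of data collection 27 May 2019" and "End of data collection 19 September 2022". Section 7.2.3 states: "The re-examination period is from 20 September 2018 to 19 September 2022". Section 7.7 adds: "Analysis will be performed for the pooled data collected by each investigator during the re-examination period".

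**Enrolment and follow-up.** Protocol 7.2.5 states: "Patients will be enrolled by continuous registration method". On follow-up it says "The investigators will collect relevant data from the time of initiating administration of Xeljanz until 24 weeks of treatment (52 weeks of treatment for the", where the longer figure applies to patients classed as long-term users. The visible text gives no closing date for enrolment. Parts of the text after 7.2.3 and before 7.6 are redacted.

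**Safety.** SAP 4.1 bases safety on "all AEs that occur during the 24 weeks (52 weeks for the long-term users) from the first treatment". SAP 3.1 requires one dose and some safety follow-up, with no minimum duration. SAP 6.2 reports the number of subjects with AEs, the incidence with a 95% CI and the number of events. It has no person-time or time-to-event method.

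**Effectiveness.** SAP 3.2 admits patients "whose efficacy data are available after 24 weeks of treatment, or based on the last assessment performed at the time of treatment discontinuation". Its exclusion list removes patients outside the safety set, those with no overall rating or a rating of not assessable, and those treated for less than 56 days.

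**The concern.** A proportion of patients with an AE can be read only if the reader knows over what time each patient was at risk. Here that time varies for three reasons:

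- A patient who starts shortly before 19 September 2022 may be observed for a few weeks.
- A patient who starts earlier is observed for 24 weeks.
- A long-term user is observed for 52 weeks.

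All three count equally in one denominator. AE incidence is the quantity of primary interest (Protocol 7.7.1). The pooled figure is neither a 24-week nor a 52-week risk, and it would change with the accrual pattern and the share of long-term users even if the drug's risk did not.

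For effectiveness the gap is narrower. A patient still on drug at data end after 8 to 24 weeks has neither 24-week data nor a discontinuation assessment, so does not meet the entry rule of SAP 3.2. If the investigator has given an assessable rating, however, no listed exclusion removes that patient. The two halves of the section give different denominators for the final effective rate.

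**Working it through.** The documents give no truncated share, accrual curve or AE rate, so there is no plan figure to reproduce. The accrual patterns and AE risks below are assumptions.

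**Share cut short by the calendar**
- Inputs: start 27 May 2019 and end 19 September 2022 (Protocol section 4), which is 1,211 days; 24 weeks = 168 days.
- The last first dose that allows 168 days is 19 September 2022 minus 168 days = 4 April 2022. Counting the day of first dose as day 1 moves this by one day.
- Uniform accrual to the last day: 168/1211 = 13.9%.
- Linearly rising accrual: 1 − (1 − 168/1211)² = 25.8%.
- Linearly falling accrual: (168/1211)² = 1.9%.
- Enrolment closed by 4 April 2022: 0%.

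These are shares with too little calendar time left. Some of these patients may stop treatment before data end for other reasons.

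**Effect of truncation alone on crude AE incidence**

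Let p be the true 24-week risk, with constant hazard λ = −ln(1 − p)/168. Under uniform accrual, truncated patients have follow-up spread evenly over 0 to 168 days. Their mean risk is m = 1 − p/(−ln(1 − p)), and the crude incidence is p − 0.139 × (p − m).

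| True p | m | Crude | Relative change |
|---|---|---|---|
| 10% | 5.1% | 9.3% | −6.8% |
| 30% | 15.9% | 28.0% | −6.5% |
| 40% | 21.7% | 37.5% | −6.4% |
| 50% | 27.9% | 46.9% | −6.1% |

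With early-weighted events (Weibull shape 0.5) the shortfall is about 4-5% for p from 2% to 50%. Under rising accrual, p = 40% gives 35.1%, about −12%.

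**Adding the 52-week windows**

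Under the same hazard the 52-week risk is F52 = 1 − (1 − p)^(52/24). A long-term share q adds q × (F52 − p). Protocol section 5 plans for at least 20% long-term users. For p = 40%, F52 = 66.9%:
- Uniform accrual, q = 20%: 37.5% + 0.20 × 26.9% ≈ 42.8%, above 40%.
- Uniform accrual, q = 5%: 37.5% + 0.05 × 26.9% ≈ 38.8%, below 40%.
- Rising accrual, q = 10%: 35.1% + 0.10 × 26.9% ≈ 37.8%, below 40%.

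With q = 20% and uniform accrual, a true 10% becomes 11.4% and a true 30% becomes 32.8%. The long-term share at which the two effects cancel, (p − crude)/(F52 − p), is about 6-11% for p from 5% to 50%. The sign of the net shift therefore depends on quantities that the plan does not fix.

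**Effectiveness**

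Under uniform accrual, 56/1211 = 4.6 points of the 13.9 have less than 8 weeks and are excluded by SAP 3.2. The remaining (168 − 56)/1211 = 9.2 points have 8 to 24 weeks and fall in the gap between entry rule and exclusion list.

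**The case against.** A reader might infer that about 14% of patients cannot reach week 24 and that the AE incidence is therefore biased downward. The documents do not support either statement as a fact.

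- **The 14% is conditional.** It needs enrolment open to the last day and uniform accrual, and neither is stated. A closing date may be in the redacted text. Protocol 7.2.5.1 allocates a number of cases to each site by contract, so a site could fill its quota early. This stands, and it is why a range from 0% to about 26% is given.
- **The sign is not established.** The 52-week windows can outweigh truncation, as shown above. This stands.
- **A 24-week risk is not the declared target.** Protocol 7.7.1 speaks of AEs investigated during the re-examination period. This stands in part: the plan does not claim a 24-week cumulative risk. But Protocol 7.3.1 and SAP 4.1 do set 24-week and 52-week windows, and the pooled proportion corresponds to neither.
- **Truncated patients do not generally stay in the week-24 effectiveness counts.** Remission, response and mucosal healing use visit windows of ±15 days without imputation (SAP 5.2.1, 6.3), and exposure under 56 days is excluded. This stands. Only the final investigator rating is affected.
- **The shift is small against sampling error.** At 40% incidence the 95% CI half-width, 1.96 × √(0.4 × 0.6/n), is about 10 points for 90 patients (18 cases at 20%, Protocol section 5) and about 4 points for the 600 in SAP 2.4. Truncation alone shifts the figure by 2.5 points. This limits the urgency, but a confidence interval does not cover a shift of unknown direction.

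A separate first-dose cut-off for the 52-week results would add nothing, because SAP 3.4.1 already requires 364 days of treatment.

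**Conclusion.** The concern holds in this form: the primary AE incidence is a crude proportion over unequal follow-up, with no minimum duration and no time-to-event method, and it matches no defined window. Truncation alone would lower it by about 6-7% relative, assuming a constant hazard and uniform accrual to data end. That shortfall is about 4-5% if events come early and about 12% under rising accrual with p = 40%. It is nil if enrolment closed by 4 April 2022. The 52-week windows act in the opposite direction, so the net bias has no known sign. Separately, SAP 3.2 contradicts itself on patients still on drug at data end with 8 to 24 weeks of exposure. The effect is modest, but it touches the primary result and is cheap to correct.

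**What to change.** 1. **SAP 6.2.** Keep the all-patient AE tables. Add a 24-week AE incidence that counts only events through day 168. Either use Kaplan-Meier with censoring at the end of each patient's follow-up, or give a proportion in patients first dosed on or before about 4 April 2022. Both remove the truncation and the 52-week mixture. The Kaplan-Meier version uses everyone but treats censoring as uninformative, which is reasonable for data end and less so for early discontinuation. The date rule does not depend on outcome.
2. **Reporting.** State the last first-dose date and the number of patients whose follow-up was cut short by the end of data collection.
3. **SAP 3.2.** Reconcile the entry rule with the exclusion list for patients still on drug at data end with 8 to 24 weeks of exposure. Show the final effective rate with and without them.

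The cost is SAP wording and one extra set of tables. Treatment dates and AE onset dates are already on the CRF (Protocol 7.2.5.3, 7.3.1.1), and SAP 5.2.2 already relies on a last follow-up date. SAP 5.1 allows a changed method to be described in the final report. The restricted version has a slightly smaller denominator. No AE is lost, because the all-patient tables stay.

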5. RATIONALE AND BACKGROUND

Xeljanz® (tofacitinib) is a potent, oral janus kinase inhibitor. Xeljanz was initially approved by the Ministry of Food and Drug Safety (MFDS) on 02 April 2014 for the treatment of adult patients with moderately to severely active rheumatoid arthritis (RA) who have had an inadequate response or intolerance to methotrexate. On 20 September 2019, new indications for the treatment of adult patients with moderately to severely active ulcerative colitis (UC) and psoriatic arthritis (PsA).

In clinical trials conducted on patients with moderately to severely active ulcerative colitis, the Xeljanz® (tofacitinib) demonstrated its efficacy and safety in adult patients who have had an inadequate response or intolerance to the basic treatments or biological agents. Ulcerative colitis has the chronic nature of relapse and improvement, most patients experience a number of acute deterioration throughout their life, and in the course of treatment with various drugs, they become resistant to or lose response to the treatment. Currently, there are very limited treatment options available to patients with moderately to severely active ulcerative colitis in terms of efficacy, safety, convenience of administration and quality of life (QoL). Therefore, for patients with limited options who do not respond to current available drugs, there are still many unmet needs for effective and rapid medications with new mechanisms of action.

CCI

Patients who are treated with Xeljanz for at least 52 weeks will be classified as long-term users. Out of all the enrolled patients, at least 18 cases (20%) of long-term users will be followed up to see the long term safety and effectiveness of Xeljanz. This non-interventional post-marketing surveillance (PMS) study is a commitment to MFDS.

6. RESEARCH QUESTION AND OBJECTIVES

The objective of this study is to identify any safety and effectiveness of Xeljanz during the post-marketing period as required by the regulation of MFDS.

7. RESEARCH METHODS

7.1. Study design

This is an open-label, non-comparative, non-interventional, prospective, and multi-center study conducted in Korean health care centers by accredited physicians (ie, investigators). The study population will be adult patients with moderately to severely active UC who have had an inadequate response or intolerance to the basic treatments or biological agents. Clinical Severity of Ulcerative Colitis is classified as mild, moderate, or severe based on the Mayo score of Partial Mayo score. (Table 1).

Table 1. Mayo Score for ulcerative colitis⁴

Variables/Score		Criteria
Stool frequency	0	Normal number of stool
	1	1-2 stools more than normal
	2	3-4 stools more than normal
	3	≥5 stools more than normal
Rectal bleeding	0	No blood seen
	1	Streaks of blood with stool less than half the time
	2	Obvious blood with stool most of the time
	3	Blood alone passed
Findings of proctosigmoidoscopy	0	Normal or inactive disease
	1	Mild disease (erythema, decreased vascular pattern, mild friability)
	2	Moderate disease (marked erythema, absent vascular pattern, friability, erosions)
	3	Severe disease (spontaneous bleeding, ulceration)
Physician's global assessment	0	Normal
	1	Mild
	2	Moderate
	3	Severe

Xeljanz will be administered according to the “Dosage and Administration” of the approved labeling. There is no visit or activity mandated by this study. The investigator will collect patient data and record the information on each patient’s case report form (CRF).

Each investigator will sequentially enroll all patients to whom Xeljanz is prescribed for the first time according to the local product label, and who agree to participate in this study by signing the data privacy statement. Safety is the primary endpoint of this study, which will be assessed based on adverse events (AEs) that have occurred between the first dose of Xeljanz to the next visit.

As a secondary endpoint, the investigator will perform the final effectiveness evaluation based on the clinical impression plus the Mayo score or Partial Mayo score. The Mayo score or the Partial Mayo Score at week 8, 16 and 24(also 52 for the long-term users) is assessed to see the remission, clinical response or mucosal healing. To assess the effectiveness of the Xeljanz. Mayo score is based on a total score of 12 points by evaluating and calculating the four clinical evaluation criteria: Stool frequency, Rectal bleeding, Findings of endoscopy, and Physician's global assessment. (Table 1) Partial Mayo Score is calculated by the sum of the remaining evaluations, except for the findings of endoscopy score.

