7.3. Variables

7.3.1. Safety variables

Safety will be assessed by the investigator based on all AEs that occur during the 24 weeks (52 weeks for the long-term users) from the first treatment for all patients who have received at least 1 dose of Xeljanz according to the local product document.

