9.2. Reporting period

For each patient, the safety event reporting period begins at the time of the patient's first dose of Xeljanz or the time of the patient's data privacy statement if s/he is already exposed to

Xeljanz, and lasts through the end of the observation period of the study which must include at least 28 calendar days following the last administration of Xeljanz; a report must be submitted to Pfizer Safety (or its designated representative) for any of the types of safety events listed in the table above occurring during this period. If a patient was administered a drug under study on the last day of the observation period, then the reporting period should be extended for 28 calendar days following the end of observation.

Most often, the date of data privacy statement is the same as the date of enrollment. In some situations, there may be a lag between the dates of data privacy statement and enrollment. In these instances, if a patient provides data privacy statement but is never enrolled in the study (eg, patient changes his/her mind about participation), the reporting period ends on the date of the decision to not enroll the patient.

If the investigator becomes aware of a SAE occurring at any time after completion of the study and s/he considers the SAE to be related to Xeljanz, the SAE must also be reported to Pfizer Safety.

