## **Statistical Analysis Plan for rPMS**

[Table 1] Mayo Score for ulcerative colitis

Variable/Score	Criteria
Stool frequency	0 Normal number of stool 1 1-2 stools more than normal 2 3-4 stools more than normal 3 $\geq$ 5 stools more than normal
Rectal bleeding	0 No blood seen 1 Streaks of blood with stool less than half the time 2 Obvious blood with stool most of the time 3 Blood alone passed
Findings of proctosigmoidoscopy	0 Normal or inactive disease 1 Mild disease(erythema, decreased vascular pattern, mild friability) 2 Moderate disease(marked erythema, absent vascular pattern, friability, erosions) 3 Severe disease(spontaneous bleeding, ulceration)
Physician's global assessment	0 Normal 1 Mild 2 Moderate 3 Severe

Xeljanz® will be administered according to the “Dosage and Administration” of the approved labeling. There is no visit or activity mandated by this study. The investigator will collect patient data and record the information on each patient's Case Report Form (CRF).

Each investigator will sequentially enroll all patients to whom Xeljanz® is prescribed for the first time according to the local product label, and who agree to participate in this study by signing the data privacy statement. Safety is the primary endpoint of this study, which will be assessed based on Adverse Events (AEs) that have occurred between the first dose of Xeljanz® to the next visit.

As a secondary endpoint, the investigator will perform the final efficacy evaluation based on the clinical impression plus the Mayo score or partial Mayo score. The Mayo score or the partial Mayo Score at week 8, 16 and 24 (also 52 for the long-term users) is assessed to see the remission, clinical response or mucosal healing. To assess the efficacy of the Xeljanz®, Mayo score is based on a total score of 12 points by evaluating and calculating the four clinical evaluation criteria: Stool frequency, Rectal bleeding, Findings of endoscopy, and Physician's global assessment [Table 1]. Partial Mayo Score is calculated by the sum of the remaining evaluations, except for the findings of endoscopy score.

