## 6.2. Safety Analyses

Safety analyses will be performed based on data of safety analysis set. All adverse events in CRF will be classified by SOC and PT according to the latest version of MedDRA.

- 1) All adverse events investigated after administration of Xeljanz® during the study will be summarized with the number of subjects having adverse events, incidence of adverse events with 95% confidence interval (C.I) and the number of adverse events by categorizing as follows:
  - Serious adverse events and serious adverse drug reactions
  - Unexpected serious adverse events and unexpected serious adverse drug reactions
  - Unexpected adverse events and unexpected adverse drug reactions
  - Adverse events and adverse drug reactions
  - Adverse events of safety concerns\*

\*Adverse event with important identified risks and important potential risks in relation to the safety specification under the risk management plan

- 2) All adverse events investigated after administration of Xeljanz® during the study will be summarized with the frequency and percentage of adverse events by categorizing as follows:
  - Occurrence status of adverse events by their severity
    - Mild
    - Moderate
    - Severe
  - Occurrence status of adverse events by their outcome
    - Recovered
    - Recovered with sequelae
    - Recovering
    - Not recovered
    - Unknown

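### The primary safety endpoint ends at an unscheduled next visit in the design sections but at 24 or 52 weeks in the endpoint sections, and the crude AE incidence pools unequal follow-up

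*Protocol*

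**What the plan says.** The design sections end the endpoint at a visit. Protocol 7.1 names safety as the primary endpoint, "which will be assessed based on adverse events (AEs) that have occurred between the first dose of Xeljanz to the next visit"; SAP 2.2 likewise rests it on "Adverse Events (AEs) that have occurred between the first dose of Xeljanz® to the next visit". Protocol 7.1 also states: "There is no visit or activity mandated by this study".

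The endpoint sections give a duration. Protocol 7.3.1 assesses safety "based on all AEs that occur during the 24 weeks (52 weeks for the long-term users) from the first treatment", and SAP 4.1 has the same rule ("all AEs that occur during the 24 weeks (52 weeks for the long-term users) from the first treatment"). Protocol 7.2.5 sets data collection over the same 24 and 52 weeks.

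The analysis sections name other periods. Protocol 7.7.1 takes AEs investigated in the re-examination period, which is calendar time (20 September 2018 to 19 September 2022 in Protocol 7.2.3). SAP 6.2 states: "All adverse events investigated after administration of Xeljanz® during the study will be summarized".

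Protocol 9.2 runs safety reporting to at least 28 days after the last dose. For a patient dosed on the last day of observation, "then the reporting period should be extended for 28 calendar days following the end of observation". Protocol 7.3.1.1 refers to Section 9.2 for the period in which AEs go on the CRF.

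Protocol 5 and SAP 3.4 define long-term users as treated for at least 52 weeks. Protocol 7.7.2 and SAP 6.1.6 also speak of long-term users who do not complete 52 weeks.

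**The concern.** AE incidence with its 95% CI is the primary result, and three things about it are loose.

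- **Endpoint wording.** The sentence that names the primary endpoint gives it an end that the study does not schedule, and it contradicts the endpoint sections.
- **Counting rule.** Neither Protocol 7.7.1 nor SAP 6.2 says whether events in the 28-day tail enter the incidence. Because long-term user has two senses, the window for a patient who stops between weeks 24 and 52 could end at week 24 or later. Two programmers could count different events.
- **Unequal follow-up.** The window length depends on persistence after baseline. The chi-square or Fisher tests and the logistic regression (SAP 6.2, items 3 and 4) use the crude yes/no outcome. A baseline factor linked to staying on treatment can therefore look like an AE risk factor merely because those patients were observed longer.

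**Working it through.** The documents give no expected AE rate and no power calculation, so there is no planned figure to reproduce. What follows is an illustration.

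**Inputs from the documents:** windows of 24 and 52 weeks; a long-term share of at least 20% (Protocol 5); N = 18/0.20 = 90 (Protocol 5) and N = 600 (SAP 2.4). These two sizes disagree, so both are shown.

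**Assumed:** first-AE hazard λ of 0.5, 0.8 or 1.2 per patient-year, either constant or halved after week 24; 20% of patients stopping at week 8 and followed to week 12; the subgroup splits below.

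**Risk by week w:** R(w) = 1 − exp(−λw/52). With the halved late hazard and w > 24, the exponent is −[24λ/52 + 0.5λ(w − 24)/52].

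**Overall incidence compared with a common 24 weeks**
- Long-term share alone: 0.8R(24) + 0.2R(52) − R(24).
- Net of early stopping: 0.6R(24) + 0.2R(52) + 0.2R(12) − R(24).
- Counting or not counting weeks 24–38 for 10% of patients who stop at week 38: 0.10[R(38) − R(24)].
- CI half-width: 1.96√(p(1 − p)/N), with p = R(24).

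For λ = 0.8 and constant hazard, R(12) = 0.169, R(24) = 0.309 and R(52) = 0.551. The net shift is 0.6(0.309) + 0.2(0.551) + 0.2(0.169) − 0.309 = 0.020.

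| | λ = 0.5 | λ = 0.8 | λ = 1.2 |
|---|---|---|---|
| R(24), % | 20.6 | 30.9 | 42.5 |
| Long-term share alone, points | +3.7 | +4.8 | +5.5 |
| Net shift, constant hazard, points | +1.8 | +2.0 | +1.8 |
| Net shift, halved late hazard, points | +0.1 | −0.1 | −0.5 |
| Week-38 stoppers, constant, points | 1.0 | 1.3 | 1.6 |
| Week-38 stoppers, halved, points | 0.5 | 0.7 | 0.9 |
| CI half-width, N = 90, points | 8.4 | 9.5 | 10.2 |
| CI half-width, N = 600, points | 3.2 | 3.7 | 4.0 |

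**Factor analyses.** Take two equal groups with the same hazard but different long-term shares a and b. Their crude incidences are (1 − a)R(24) + aR(52) and (1 − b)R(24) + bR(52). For λ = 0.8 with 10% versus 30%, these are 0.333 and 0.381, so OR = (0.381/0.619)/(0.333/0.667) = 1.23. Rejection is the chance that a 5% chi-square test is significant with 45 or 300 per group.

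| Long-term shares | Late hazard | Spurious OR | Rejects, N = 90 | Rejects, N = 600 |
|---|---|---|---|---|
| 10% v 30% | constant | 1.23–1.25 | 7–8% | 19–28% |
| 10% v 30% | halved | 1.12–1.14 | about 6% | 9–13% |
| 15% v 25% | constant | 1.11–1.12 | 5–6% | 8–11% |
| 15% v 25% | halved | 1.06–1.07 | 5–6% | 6–7% |

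**Does a 24-week window cure this?** Only in part. With 30% versus 10% stopping early and followed to week 12, compare 0.7R(24) + 0.3R(12) with 0.9R(24) + 0.1R(12). The OR is 1.14, 1.15 and 1.17 for the three hazards. A first-event rate does not have this problem under a constant hazard. Expected person-time to week w is R(w)/λ years, so events over person-time return λ (50, 80 and 120 per 100 patient-years) whatever the follow-up mix.

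**The case against.** Both endpoint sections give the same window and data collection matches it, so the next-visit phrase is a leftover with an evident resolution. That is right. A reader might infer that the primary endpoint has no time window at all, and the documents do not support that. What stands is that the phrase is wrong as written in both documents and that the analysis sections do not restate the window.

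A reader might also infer that patients who stop between weeks 24 and 52 are definitely cut off at week 24 by SAP 4.1 while SAP 6.2 counts their later events. That does not follow. Protocol 7.7.2 and SAP 6.1.6 can be read as giving them the 52-week window. On the stricter definition, Protocol 7.2.5 would also end their data collection at week 24. The supportable point is that the term has two senses.

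The study is descriptive, single-arm and shaped by regulation (Protocol 7.8). SAP 6.4 analyses long-term users separately and SAP 6.1.5 tabulates treatment duration. These help in part: the main safety set still mixes follow-up lengths, and exposure is not linked to incidence. SAP 5.1 and 6.2 also specify two-sided 5% tests and odds ratios, so the factor results will be read as more than description.

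**Conclusion.** The wording conflict, the missing rule for tail events and the double use of long-term user are certain from the text. The pooling of unequal follow-up is also certain; its size depends on the assumed hazards and shares.

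It would be tempting to conclude that the headline incidence is materially biased. The figures do not show that: the net shift is about 2 points or less, within the sampling error at either size.

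The factor analyses are more exposed, but the highest rejection rates (19–28%) need N = 600, a 10% versus 30% split and a constant hazard together. Across all cases shown, rejection is about 5–8% at N = 90 and 6–28% at N = 600. This should be fixed, but it does not undermine the study.

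**What to change.** - Delete the next-visit wording from Protocol 7.1 and SAP 2.2 so that they match Protocol 7.3.1 and SAP 4.1. Align the periods named in Protocol 7.7.1 and SAP 6.2 with that window.
- In SAP 6.2, say whether events in the 28-day tail count. Reconcile the two senses of long-term user, so that counting is defined for patients who stop between weeks 24 and 52.
- Add the AE incidence over the first 24 weeks from first dose for the full safety set. Run items 3 and 4 on first-24-week events, without a post-baseline exposure covariate.
- Add a first-event rate or cumulative incidence, overall and by subgroup, because the window alone leaves the early-stopping distortion.
- Define end of follow-up for discontinued patients from dates actually collected, for example treatment stop date plus the 28-day reporting tail. The last follow-up date in SAP 5.2.2 only imputes treatment end for patients still on drug.
- Keep the existing all-AE tables and report later events for everyone still followed, so that no safety data are lost.

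**Cost.** A protocol amendment where Protocol 7.7 requires one, with IRB/IEC approval where applicable (Protocol 8.3), plus a counting rule and one or two added tables. Treatment dates and AE onset dates are already on the CRF (Protocol 7.2.5.3 and 7.3.1.1). SAP version 1.1 (2 November 2022) postdates the planned end of data collection (19 September 2022), so the changes should rest on data already held. The headline incidence may change slightly.
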